6.5 Efficacy Analysis

6.5.1 Primary Analysis of Progression-Free Survival

Progression-free survival is defined as the time from randomization to the occurrence of disease progression as assessed by the IRC using RECIST v1.1 or death from any cause, whichever occurs first. Patients who have not experienced disease progression or death at the time of analysis of PFS will be censored at the date of the last evaluable radiographic disease assessment. The duration of primary analysis of PFS will be censored as outlined in Table 4. The sensitivity analysis will be performed if > 5% of patients have a PFS event immediately after missing at least two scans consecutively before the data cutoff, by considering such as event at the first date of documented progression or death.

Treatment comparisons will be based on the stratified log-rank test in the ITT population. The stratification factors will be those used for randomization and will be obtained from the IWRS (prior PD-1/PD-L1 inhibitor therapy [yes vs. no] and IMDC prognostic risk group [favorable vs. intermediate vs. poor]). A 2-sided $p \leq 0.05$ in favor of the CB-Cabo experimental treatment will be regarded as a positive result for the study. The null and alternative hypotheses can be phrased in terms of the survival functions $S_{PFS_CB-Cabo}(t)$ and $S_{PFS_Pbo-Cabo}(t)$ in arm CB-Cabo and arm Pbo-Cabo, respectively:

$$H_0: S_{PFS_CB-Cabo}(t) = S_{PFS_Pbo-Cabo}(t) \text{ versus } H_1: S_{PFS_CB-Cabo}(t) \neq S_{PFS_Pbo-Cabo}(t)$$

Kaplan-Meier methodology will be used to estimate median PFS for each treatment arm and construct survival curves for the visual description of the difference between the treatment arms. The Brookmeyer-Crowley methodology will be used to construct the 95% CI for the median PFS for each treatment arm (1).

The hazard ratio (HR), $\lambda_{PFS_CB-Cabo}/\lambda_{PFS_Pbo-Cabo}$, where $\lambda_{PFS_CB-Cabo}$ and $\lambda_{PFS_Pbo-Cabo}$, represents the hazard of PFS in arm CB-Cabo and arm Pbo-Cabo, respectively. HR will be estimated with a stratified Cox proportional hazards regression model and the same stratification variables used for the stratified log-rank test. In addition, as a sensitivity

analysis for the primary endpoint, the above analyses will be repeated with only two levels, i.e., favorable vs. intermediate/poor, for the IMDC Prognostic Risk grouping.

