To prevent a stratification cell having too few events, if a stratification cell has less than 10 PFS events (two arms combined), the stratification factor that contributes the least number of events for that cell will be removed. Stratification factors for the analyses will be removed until all stratification cells have at least 10 PFS events in two arms combined.

As a sensitivity analysis, the above analyses will be performed using the number of prior TKI cancer therapy (0 vs. ≥ 1) and IMDC prognostic risk group (favorable vs. intermediate vs. poor) and prior PD-1/PD-L1 inhibitor therapy as the stratification factors.

If there is notable imbalance in number of prior lines of anti-cancer therapy between the two treatment arms and if sample size permits, sensitivity analysis will be performed using number of prior lines of anti-cancer therapy (1 vs. 2) and IMDC prognostic risk group (favorable vs. intermediate vs. poor) and prior PD-1/PD-L1 inhibitor therapy as the stratification factors.

Similarly to the primary analysis, to prevent a stratification cell having too few events, if a stratification cell has less than 10 PFS events (two arms combined), the stratification factor of prior PD-1/PD-L1 inhibitor therapy will be removed.

Results from an unstratified analysis will also be provided.

Table 4 Censoring Rules for Progression Free Survival

Situation	Date of PFS Event or Censoring	Outcome
No baseline disease assessment	Date of randomization	Censored
No post-baseline assessments and no death	Date of randomization	Censored
No progression and no death	Date of last evaluable tumor assessment	Censored
Additional cancer therapy prior to documentation of disease progression or death	Date of last evaluable tumor assessment before initiation of additional cancer therapy	Censored
Documented RECIST v1.1 progression or death between scheduled visits [1]	First date of documented progression or death	PFS event
RECIST v1.1 progression or death documented to occur following missing at least 2 consecutive scheduled radiographic disease assessments (including missing assessments, insufficient data for the assessments, and an overall response of non-evaluable) following previous evaluable radiologic tumor assessment	Date of last tumor assessment with no documented progression [2]	Censored [2]

RECIST v1.1, Response Evaluation Criteria in Solid Tumors Version 1.1

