[1] RECIST v1.1 progression or death can occur either on treatment or during the survival follow up period.

[2] Sensitivity analysis with status of PFS event at the first date of documented progression or death.

$$\text{PFS (month)} = (\text{date of event / censor} - \text{date of randomization} + 1) / 30.4375$$

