Patient-reported outcomes (PRO) for the NCCN-FACT FKSI-19 (Version 2) will be summarized by treatment group. Summary statistics (mean, SD, median, range) of the change from baseline will be provided at each time point. Mean score for each endpoint will be displayed graphically. The analysis will be performed for patients in the PRO-evaluable population, which is defined as ITT with a non-missing baseline assessment and at least one non-missing post-baseline assessment until treatment discontinuation.

With the exception of the visual analog scale (VAS) score and index score for EQ-5D-5L questionnaire, descriptive statistics summarizing the proportions of patients who reported having “no,” “slight,” “moderate,” “severe,” or “extreme/unable” problems at each time point will be reported. The VAS score and the US-specific Index score for EQ-5D-5L questionnaire will be summarized and analyzed as continuous measures. Patients without post-baseline assessments will be excluded from this analysis.

6.5.3.6 *Additional Sensitivity Analyses*

Missing Tumor Assessment

The impact of missing scheduled tumor assessments on PFS may be assessed depending on the number of patients who missed assessments scheduled immediately prior to the date of disease progression per RECIST v1.1. If > 5% of patients missed two or more scheduled assessments consecutively immediately prior to the date of disease progression per RECIST v1.1 in any treatment arm, the following sensitivity analyses will be performed:

Patients who missed two or more scheduled assessments immediately prior to the date of disease progression per RECIST v1.1 or the data cutoff or death will be censored at the last tumor assessment prior to the missed visits.

Statistical methodologies analogous to those used in the primary analysis of PFS as specified in [Section 6.5.1](#) will be used for this sensitivity analysis.

Loss to Follow-up

The impact of loss to follow-up on OS may be assessed depending on the number of patients who are lost to follow-up. If > 5% of patients are lost to follow-up for OS in either treatment arm, a sensitivity analysis will be performed for the comparisons between two treatment arms in which patients who are lost to follow-up will be considered as having died on the date they are lost to follow-up.

6.5.3.7 *Subgroup Analyses*

The consistency of the primary PFS and secondary OS results in subgroups will be examined. The subgroups are defined by the following

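### The missing-scan PFS sensitivity analysis in SAP 6.5.3.6 in substance repeats the primary censoring, and its 5% condition conflicts with the one on the event-counting analysis in 6.5.1

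*SAP*

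**What the plan says.** **Primary rule.** SAP Table 4 censors a progression or death that follows at least two consecutive missed scheduled assessments, at the last assessment without progression. It counts as missed "including missing assessments, insufficient data for the assessments, and an overall response of non-evaluable", and it requires an earlier evaluable tumor assessment before the gap. Protocol 14.6.1 has the same rule without that last qualifier. Patients with no event at the cutoff are censored at their last evaluable assessment.

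**SAP 6.5.3.6, Missing Tumor Assessment.** The purpose is given as "The impact of missing scheduled tumor assessments on PFS may be assessed". The condition is that more than 5% of patients missed two or more consecutive scheduled assessments "immediately prior to the date of disease progression per RECIST v1.1 in any treatment arm". The rule is that patients with two or more missed assessments immediately before progression "or the data cutoff or death will be censored at the last tumor assessment prior to the missed visits". Methods are to be analogous to those of the primary analysis.

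**SAP 6.5.1.** The condition reads: "The sensitivity analysis will be performed if > 5% of patients have a PFS event immediately after missing at least two scans consecutively". Only what happens up to the cutoff counts towards it. The censored record is then changed, in the SAP's words, "by considering such as event at the first date of documented progression or death".

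**Table 4 footnote [2].** "Sensitivity analysis with status of PFS event at the first date of documented progression or death". No threshold is given.

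**The concern.** A sensitivity analysis for a censoring rule has to change that rule. The one in 6.5.3.6 keeps it, so a result close to the primary is largely built in and could be reported as robustness when nothing was tested.

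The analysis that does change the rule exists, but whether it runs depends on which passage the programmer follows. This matters more because SAP 6.9.2.1 leaves scans missed through COVID-19 to the Table 4 handling. SAP 6.9.1 adds by-arm summaries and optional analyses, but no specified PFS analysis that counts progression or death after a gap. The analysis in 6.5.1 and footnote [2] is therefore the only specified one that does.

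**Working it through.** **1. Context figure.** The plan's event count, for HR 0.69, two-sided 0.05 and power 0.85, is 4 × (1.960 + 1.036)² / (ln 0.69)² = 35.91 / 0.1377 ≈ 261, against 262 stated. It reproduces, and nothing below changes it.

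**2. The two censoring rules side by side.**

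| History | Primary (Table 4) | 6.5.3.6 |
|---|---|---|
| Evaluable post-baseline scan, two or more scheduled scans not done, no scan in the gap, then progression or death | Censored at last scan before the gap | Same |
| Same gap, event-free at cutoff | Censored at last evaluable scan | Same |
| Gap made of insufficient or non-evaluable scans, then an event | Censored | Not named as missed; may count as an event if 6.5.3.6 replaces the Table 4 row |
| Earlier gap, then an evaluable scan, then an event | Censored if Table 4 is read to cover any earlier gap | Gap is not immediately before the event; may count as an event if 6.5.3.6 replaces the row |
| Evaluable unscheduled scan inside the gap | Read literally, censored at that scan | Censored before the gap |
| First two post-baseline scans missed, then death | May be an event if baseline is not the required earlier evaluable assessment | Censored |

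I coded both rules on every history of 0 to 6 scheduled scans (evaluable, missing or non-evaluable) ending in progression, death or cutoff: 3 × (1 + 3 + 9 + 27 + 81 + 243 + 729) = 3,279 histories. Using Table 4's definition of missed and a gap immediately before the end, the rules differ in 0. The event-counting rule of 6.5.1 differs from the primary in 968. This check treats baseline as evaluable and has no unscheduled scans, so it does not cover the last two rows of the table; those come from reading the text.

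In no row does 6.5.3.6 count as an event a progression or death that directly follows two scans not done.

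**3. The three conditions.**

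| Place | Unit | Event type | Threshold |
|---|---|---|---|
| 6.5.1 | No arm named | Progression or death | >5% |
| 6.5.3.6 | Any one arm | Progression only | >5% |
| Footnote [2] | – | Progression or death | None stated |

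With 416 patients, 208 per arm (protocol 6.0), and all randomized patients as denominator:

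- 6.5.3.6: 0.05 × 208 = 10.4, so 11 progressions in one arm.
- 6.5.1 read as pooled: 0.05 × 416 = 20.8, so 21 events. Up to 20 can be censored without reaching it: 20/416 = 4.8%, or 20/208 = 9.6% of an arm if all fall in one.
- 13 versus 6 progressions, no deaths: 13/208 = 6.25% and 19/416 = 4.6%. Only 6.5.3.6 runs.
- 10 progressions and 1 death in each arm: 10/208 = 4.8% and 22/416 = 5.3%. Only 6.5.1 runs.
- 6.5.1 read per arm: 11 progressions in an arm meet both conditions, so 6.5.3.6 cannot run alone.

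**4. How often the conditions disagree (pooled 6.5.1, footnote [2] bound by it).** Exact enumeration of independent binomial counts, n = 208 per arm. The documents give no post-gap rates, so all rates are assumptions. Each cell gives only 6.5.3.6 runs / only 6.5.1 runs.

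| Post-gap progression rate (arm 1, arm 2) | No post-gap deaths | 1% deaths per arm | 2% deaths per arm |
|---|---|---|---|
| 3%, 3% | 8.3% / 0 | 3.2% / 10.1% | 0.6% / 42.0% |
| 4%, 4% | 21.5% / 0 | 5.2% / 18.4% | 0.7% / 44.3% |
| 5%, 5% | 20.4% / 0 | 3.4% / 13.5% | 0.3% / 24.1% |
| 6%, 6% | 9.5% / 0 | 1.1% / 5.2% | 0.1% / 7.8% |
| 6%, 3% | 39.7% / 0 | 11.7% / 7.9% | 1.8% / 20.0% |

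The zeros follow from arithmetic: without deaths, 21 pooled progressions force at least 11 in one arm.

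**The case against.** Four points can be made for the plan.

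- **The rules are not identical.** This stands. A reader might infer that 6.5.3.6 can never change a record. The documents do not support that: an unscheduled scan inside the gap (allowed by protocol 10.3 and SAP section 4) can move the censoring date, and a death after the first two missed post-baseline scans could be censored by 6.5.3.6 but counted by Table 4. These are narrow cases, and none makes 6.5.3.6 a test of the censoring of events after scans not done.
- **The informative analysis is already specified, in two places.** This also stands, so it would be wrong to infer that the plan lacks one. If footnote [2] is read as unconditional, it always runs and the practical harm disappears. What remains is that 6.5.1 puts a condition on it and the footnote does not.
- **The harmful mismatch needs particular rates.** Correct. With 2% post-gap deaths per arm it is below 1% at equal progression rates, and the harmless mismatch, where only the informative analysis runs, is far more common. Two post-gap deaths added to the 13 versus 6 example bring the pooled count to 21 and remove it.
- **Nothing confirmatory rests on 6.5.3.6.** Correct. A reader might go on to infer that the primary hazard ratio or power is compromised. That would be a challenge to the Table 4 censoring choice itself, which is a separate matter; the defect here does not move either.

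**Conclusion.** The point holds in this form. SAP 6.5.3.6 in substance repeats the primary censoring and cannot serve its stated purpose for events that directly follow scans not done. The conditions in 6.5.1, 6.5.3.6 and footnote [2] conflict in unit, event type and existence; the event-type conflict and the footnote's silence do not depend on any assumption.

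The consequence that the uninformative analysis runs alone is conditional. It needs 6.5.1 read as pooled, footnote [2] read as subject to the 5% condition, and few post-gap deaths. The pooled reading is natural, because 6.5.3.6 names arms where it means arms, but it is not stated. Under those readings the chance at equal progression rates of 3 to 6% is about 8 to 21% with no post-gap deaths, 1 to 5% with 1% deaths per arm, and under 1% with 2%.

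This is a defect in the specification of sensitivity analyses. It should be fixed before the primary analysis.

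**What to change.** In SAP 6.5.3.6, delete the missing-assessment condition and the censoring sentence, and refer to 6.5.1.

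In 6.5.1, state one event-counting analysis. Progression or death after at least two consecutive scheduled assessments that were missed in Table 4's sense (not done, insufficient or non-evaluable) is a PFS event at the first documented date, with every other Table 4 row unchanged. Either run it without a threshold, as footnote [2] reads, or give it one condition that is met when either arm exceeds 5% and that counts both progressions and deaths. Make footnote [2] match. Tabulate the affected patients by arm and by event type.

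The cost is SAP wording, at most one extra analysis run and one small table. It needs no new data and leaves the primary analysis as it is.

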8.0 INCLUSION/ EXCLUSION CRITERIA

8.1 Inclusion Criteria

1. Informed Consent

- a. Ability to provide written informed consent in accordance with federal, local, and institutional guidelines

2. Target Population

- a. Documented histological or cytological diagnosis of renal cell carcinoma with a clear-cell component
- b. Age \geq 18 years
- c. Karnofsky Performance Score (KPS) \geq 70% ([Attachment 4](#))
- d. Estimated Life Expectancy of at least 3 mo
- e. Measurable Disease per RECIST 1.1 as determined by the Investigator (see [Attachment 5](#))
- f. One and not more than two prior systemic lines of therapy (monotherapy or combination regimen) for advanced or metastatic RCC
 - 1) Must include either:
 - i. one anti-angiogenic therapy (any VEGF pathway-targeted agent, used either as monotherapy or as a component of a combination regimen)
– OR –
 - ii. the combination regimen of nivolumab + ipilimumab
 - 2) Exposure to a prior treatment regimen for \geq 4 weeks is considered a prior line of therapy, regardless of reason for its discontinuation (exception: high-dose IL2 will count as prior therapy if $>$ 3 doses administered)
 - i. 4 weeks will be counted from first to last dose for regimens that are intended to be administered on daily schedules (e.g., sunitinib, pazopanib) and from first dose to end of cycle length after last dose for regimens that are intended to be administered in intervals of \geq 1 week (e.g., one treatment of a Q2W regimen counts as 2 weeks of therapy)
 - 3) Rechallenge with the same agent or regimen will not be considered a new line of therapy, if the patient had not previously discontinued that agent or regimen because of disease progression
 - 4) Systemic adjuvant therapy is considered a prior line of therapy if the patient has disease recurrence on or within 1 year after the last dose of adjuvant therapy
- g. The patient must have had radiographic evidence of disease progression on or after the most recent systemic therapy and within 6 mo before randomization

3. Laboratory Findings

- a. Serum creatinine \leq 2.0 \times upper limit of normal or calculated creatinine clearance (C_{Cr}) \geq 30 mL/min (\geq 0.5 mL/sec) using the Cockcroft-Gault equation:

$$C_{Cr} = \{((140 - \text{age}) \times \text{actual body weight}) / (72 \times S_{Cr})\} \times 0.85 \text{ (if female)}$$

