- 1) demographics (age [<75 vs ≥ 75], sex [F vs M], and race/ethnicity)
- 2) baseline prognostic characteristics (KPS performance status [70-80, 90-100], IMDC prognostic risk grouping [EDC version], number of organs with metastases [1, 2, ≥ 3], prior nephrectomy, and prior radiotherapy, time from metastatic diagnosis [>1 and ≤ 1 year])
- 3) Prior therapies (previous anti-angiogenic therapies [yes/no], number of prior TKI [1, 2, ≥ 3], prior PD-1/PD-L1 [yes, no], prior nivo/ipi [yes, no], number of prior line of therapy [2, 3])
- 4) Metastatic Sites (lung, lymph node, bone, liver, brain, other as categories)

5) Geographic region (US/ex US)

Summaries of PFS and OS, including unstratified HRs estimated from Cox proportional hazards models and Kaplan-Meier estimates of median PFS and OS, will be produced separately for each level of the categorical variables for the comparisons between treatment arms and displayed in a forest plot (Lewis 2001).

Summaries of ORR by subgroup defined above will also be provided.

Analyses of subgroups with sample size too small may not be performed.

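### The SAP 6.5.3.7 subgroup levels for prior lines (2, 3) and prior TKIs (1, 2, ≥3) do not match the eligible population or the levels used elsewhere in the SAP

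*SAP*

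**What the plan says.** Item 3 of the subgroup list in SAP 6.5.3.7 names five prior-therapy variables. Two are counts: "number of prior TKI [1, 2", with ≥3 as the last level, and "number of prior line of therapy [2, 3". The other three are yes/no: anti-angiogenic therapy, PD-1/PD-L1 therapy, and nivolumab plus ipilimumab.

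The section says that the PFS and OS summaries "will be produced separately for each level of the categorical variables" and shown in a forest plot. ORR is summarised by the same subgroups. A closing sentence covers sparse groups: "Analyses of subgroups with sample size too small may not be performed".

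Inclusion criterion 2f (Protocol 8.1) requires "One and not more than two prior systemic lines of therapy (monotherapy or combination regimen) for advanced or metastatic RCC". It can be met by either of two routes: "one anti-angiogenic therapy (any VEGF pathway-targeted agent, used either as monotherapy or as a component of a combination regimen", or "the combination regimen of nivolumab + ipilimumab".

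SAP 6.5.1 (PFS) and 6.5.2.1 (OS) both plan sensitivity analyses stratified by prior lines as 1 vs. 2, and by prior TKI as 0 vs. ≥1. The prior-lines analysis is conditional on a notable imbalance between arms and on sample size.

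**The concern.** The same SAP gives prior lines two sets of levels, and only the set in 6.5.1 and 6.5.2.1 agrees with the eligibility rule. A programmer who follows 6.5.3.7 as written could do one of two things: leave patients with one prior line out of the forest plot, or put them in a row labelled 2. Under the second choice, 2 means one prior line in the subgroup section and two prior lines in the sensitivity analyses.

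The TKI variable has a separate gap. Patients without a prior TKI are eligible by design, and Protocol 9.1 argues for admitting patients without prior anti-angiogenic therapy, but the variable has no row for them.

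The purpose of 6.5.3.7 is to check that the PFS and OS results are consistent across subgroups. A variable that omits or mislabels eligible patients cannot do this for the whole ITT population.

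**Working it through.** The plan gives no figure to reproduce here. The check compares the levels as sets.

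**Inputs**

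| Variable | Values possible under 2f | Levels in SAP 6.5.1 and 6.5.2.1 | Levels in SAP 6.5.3.7 |
|---|---|---|---|
| Prior lines | 1, 2 | 1 vs. 2 | 2, 3 |
| Prior TKIs | 0, 1, 2, ≥3 | 0 vs. ≥1 | 1, 2, ≥3 |

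**Prior lines, literal reading (lines counted as in 2f)**
- Eligible {1, 2} and listed {2, 3} overlap in {2}.
- Eligible but not listed: {1}, so 1 of 2 eligible values has no level.
- Listed but not eligible: {3}, so 1 of 2 listed levels could hold only patients who breach 2f.

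**Prior lines, read as line of study treatment**
- Line of treatment = prior lines + 1, so 1 → 2 and 2 → 3.
- 0 of 2 eligible values are lost, but as a number of prior lines 2 of 2 labels are one too high.

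**Prior TKIs**
- Zero is an eligible value. A patient may enter on nivolumab plus ipilimumab, or on a VEGF-pathway agent that is not a TKI. Protocol 9.1 names bevacizumab as one such agent.
- Possible {0, 1, 2, ≥3} against listed {1, 2, ≥3}: 3 of 4 covered, and 0 is not. This holds under either reading of prior lines.
- The ≥3 level does not conflict with 2f. That criterion limits lines, not agents, and some short or adjuvant regimens do not count as lines.

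**Do neighbouring rows close the TKI gap?** Only in part. In "previous anti-angiogenic therapies [yes/no", a patient whose only VEGF agent was bevacizumab is a yes with 0 TKIs. The nivolumab plus ipilimumab row does not isolate TKI-naive patients either, because such a patient may have had a TKI in the other line.

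**Reuse.** SAP 6.9.2.1 takes the 6.5.3.7 factors as covariates in an inverse-probability-of-censoring model if 10 or more qualifying COVID-19 deaths occur. SAP 6.9.2.2 plans similar analyses for OS.

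**After correction.** With levels {1, 2} and {0, 1, 2, ≥3}, 2 of 2 eligible line counts and 4 of 4 TKI values are covered.

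**The case against.** The strongest reply is that [2, 3] is a slip of label: the authors meant second- or third-line study treatment, which maps exactly onto one or two prior lines. The Protocol background does speak of second-line trials, and the SAP reference list includes a paper on third-line therapy. This may well be what was intended, and then no patient is lost. But neither document says so, the variable is named as a count of prior lines, and the SAP twice gives 1 vs. 2 for an almost identically named variable. The text needs correcting on either reading.

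Second, an eligible patient could reach three regimens if 6.5.3.7 counts every recorded one, because 2f does not count regimens given for less than 4 weeks or adjuvant therapy with recurrence more than a year after the last dose. That is fair: the statement that level 3 lies outside 2f depends on counting lines as 2f does. A count of all regimens would still leave out patients with one.

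Third, [1, 2] has no row for a randomized patient with three prior lines, who stays in the ITT set as a deviation. This is true, but it applies equally to the 1 vs. 2 factor already in 6.5.1 and 6.5.2.1, and it concerns deviators only.

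Fourth, a subgroup list need not place every patient, and [1, 2, ≥3] could describe extent of exposure among TKI-treated patients. Protocol 14.6.4 similarly uses 1 vs. >1 for previous anti-angiogenic therapies. But 6.5.3.7 does not restrict the variable to TKI-treated patients. The small-subgroup clause lets a listed level be skipped; it does not supply a missing one.

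Finally, the link to the COVID-19 weighting model is remote. It needs the death trigger, and the text does not say that the factors must enter with the listed levels. It is a secondary consequence only.

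**Conclusion.** The concern holds and is minor. Two of the five prior-therapy variables in item 3 have levels that do not fit the eligible population. For prior lines, either one of two eligible values has no row or both labels are one too high, depending on the reading. For prior TKIs, one of four possible values has no row on either reading.

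The effect is confined to descriptive PFS, OS and ORR subgroup summaries, with a possible conditional effect on the COVID-19 weighting covariates. The primary log-rank test, alpha, power and ITT analyses are untouched. The literal reading assumes that lines are counted as in criterion 2f. The documents give no patient numbers for these groups, so the number of patients affected cannot be stated.

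**What to change.** In SAP 6.5.3.7, change the prior-lines levels to [1, 2] and the prior-TKI levels to [0, 1, 2, ≥3]. Keep the ≥3 level and leave sparse levels to the existing small-subgroup clause. State that prior lines are counted the same way as in 6.5.1 and 6.5.2.1, and use the corrected levels wherever the 6.5.3.7 factors are reused.

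The cost is two bracketed lists and one clarifying sentence in the SAP. It needs no new data, no change to the primary analysis and no protocol amendment. Making the change before results are known avoids post hoc regrouping.
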